Exploratory Crossover Arm Guided by Electrophysiology Biomarkers. These encounters and treatment assignments occur as part of research. Based on safety and tolerability testing from the field shaping survey, we will activate a combination of one or more DBS contact segments based purely on electrophysiology from the intraoperative assay over the next two months. Similar to the randomized crossover, participants will be allowed to adjust stimulus amplitude at home during the first month, within safety constraints defined by therapeutic window measures from the field shaping survey. They will remain on their preferred amplitude for the second month of the randomization period and then return at the end for motor and non-motor assessments. Motor outcomes for the crossover will include repeat UPDRS part 3, pegboard dexterity, gait speed test, and posture/balance measures from the Motor Battery (discussed previously). Non-motor assessments will occur on a different day and include patient-reported quality of life measures, cognitive/behavioral, and speech batteries (discussed previously). At study conclusion, we will again collect data regarding patient preference, ranking the various programming strategies from the crossover study from best to worst, and explain their rationale for their treatment preference.

Study Exit = visit with repeated outpatient EEG assay: This encounter will serve as a 1 year post-operative follow up visit that would normally be a part of routine care. We will repeat the Motor Battery at this time as well. To test the long-term robustness of our electrophysiological measures we will retest the electrophysiological assay conducted 1 year prior in the operating room, measuring cortical activation by DBS with EEG and 8 contralateral surface EMG

electrodes. We will not measure ECoG during this assay because this modality is only available during surgery (we remove the ECoG strip after testing in the OR). In this post-op visit, the implanted Boston Scientific pulse generator will provide the electrical stimulation. We will elicit cortical responses from stimulation from adjacent electrode contact pairs in a similar manner to our protocol during surgery. The total duration of the assay is approximately 30 minutes.

b. What is the probable length of time required for the entire study (i.e., recruitment through data analysis to study closure)?

5 years

c. What is the total amount of time each participant will be involved?

1 year

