Success Criteria: We propose that current steering with the directional lead will yield within-participant changes in ERPs that mirror the EEG findings with omnidirectional DBS in our Supporting Data (proposal **Figs. 2-5**). Specifically, we anticipate that contacts with large therapeutic windows will display P1/N1 peak latencies of ≥ 550 μ sec (proposal **Fig. 3D**) and absence of the large amplitude HFO (proposal **Fig. 4C**). Conversely, we anticipate that contacts with small therapeutic windows will display P1/N1 latencies of < 550 μ sec and presence of the HFO. In addition to these criteria, we will also investigate whether directional stimulation alters the spatial distribution of ERP responses on the ECoG strip. Criteria for success are to demonstrate that directional stimulation yields similar quantitative changes in ERP timing and morphology within individuals.

Rationale: This milestone focuses on feasibility of using the intraoperative EEG/ECoG assay to inform the use of directional DBS technology. Initial goals are to demonstrate that directional DBS can yield within-participant changes in ERP latency, morphology, localization and other parameters with EEG/ECoG that predict behavioral responses to stimulation (SA 1.2).

Milestone 2.6: **Determine whether patient-specific *combinations* of active DBS contact segments, guided by cortical physiology versus behavior alone, acutely modify the therapeutic window during the Field Shaping Survey (SAs 2.1 and 2.2).**

Success Criteria: Demonstrate significant changes in the therapeutic window with field shaping within individuals, defined as $\geq 20\%$ improvement or worsening therapeutic window in at least one grouping of 3 electrode contact segments versus omnidirectional DBS in $\geq 40\%$ of the participants who have reached the Field Shaping Survey by the end of Y2. We will rank each of the 8 contact segments for their likelihood for efficacy (SA2.1) and motor side effects (SA2.2), based on quantitative behavioral and cortical physiology criteria. We will simultaneously activate the 3 most highly ranked contact segments for behavioral testing with effective versus adverse combinations of contacts (SAs 2.1 versus 2.2), based on these criteria. The survey will be performed in conjunction with the assessment battery after the second treatment phase. To maintain blinding, patients will not be told which survey is being performed or which treatment condition they will receive.

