Rationale: In this first-in-human approach, we will reversibly activate unique combinations of DBS contact segments, guided by cortical physiology and behavioral criteria, to explore putative biomarkers to guide field shaping with multiple directional DBS contacts. This dose-finding and safety study will directly inform contact selection for the final arm of the double-blind crossover and other related milestones.

Behavioral criteria for contact selection in SA2.1 arise from the Monopolar Survey and will be defined as the 3 lead segments with the lowest floor of the therapeutic window. As previously, if we were unable to demonstrate changes in therapeutic window floor with directional DBS either at the individual or group level in Milestone 2.4, we would instead use the three contacts that displayed the greatest therapeutic window magnitude or percent improvement in UPDRS hemibody subscore for the stimulated side of the body. Behavioral criteria for contact selection in SA2.2 will be defined as the 3 lead segments with the lowest (worst) stimulus amplitude thresholds for adverse capsular motor side effects (involuntary contraction of the mouth, arm, or leg).

Cortical physiology criteria for contact selection in SA2.1 arise from analyses of intraoperative EEG/ECoG studies in Milestone 2.3. We have previously demonstrated that within-participant changes in P1/N1 amplitude are associated with the magnitude of improvement in motor symptoms during high frequency DBS for PD and essential tremor. Thus, EEG criteria for contact selection in SA2.1 are peak latency of ≥ 550 μ sec (proposal **Fig. 3D**) and absence of the large amplitude HFO (proposal **Fig. 4C**). We will rank and simultaneously activate the 3 most promising lead segments that meet the above criteria based upon P1/N1 peak amplitude. The EEG criteria for SA2.2 are P1/N1 latency < 550 μ sec (proposal **Fig. 3D**) and presence of the HFO (proposal **Fig. 4C**). We will then rank and simultaneously activate the 3 lead segments based upon P1/N1 peak amplitude. In addition to these criteria, we will also investigate whether directional stimulation alters the spatial distribution of ERP responses on the ECoG strip.

Milestone 2.7: **Establish cognitive and behavioral safety related to directional versus omnidirectional DBS.**

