selected based cortical ERP physiology, using both therapeutic window and change in UPDRS part 3 as data nested within person. Secondary analyses will contrast the efficacy of these DBS adjustment strategies based upon changes in other elements of the Motor battery. In SA 2.3, we use the randomized, doubleblind crossover trial to compare changes in UPDRS and other measures of quality of life and motor, cognitive, behavioral, and speech function across the DBS programming strategies identified in SA 2.1. The primary statistical analysis will use Proc Mixed in SAS with active contact groupings including (1) conventional DBS, (2) multiple active contacts selected based on behavior, and (3) multiple active contacts based on ERPs as factor and patient preference and changes in PDQ-39 and UPDRS part 3 as data. Sample size for SA2. We will obtain multiple repeated measures within participants and can readily detect changes in patient preference, PDQ-39, UPDRS part 3, and other motor and non-motor variables of interest. Patient reported evidence for the hypothesis of superiority of current steering will be shown by determining that 20 or more of the 30 participants favor either current steering approach over conventional DBS using a binomial distribution based on patient preference (vote), PDQ-39, and UPDRS part 3. This would achieve a p value of < 0.049 . We will declare current steering DBS to be clinically superior to conventional therapy based on patient preference if 20 or more patients meet this criterion. We will measure the frequency by which current steering provides better outcomes versus conventional DBS, which could still be highly relevant and significant clinically (even if preferred by <20 participants). Secondary measures will quantify within-participant changes in upper limb dexterity, gait speed test, posture and balance, cognitive/behavioral measures, speech, and motor diaries. Additionally, we will contrast the probability that active contacts are shared among the programming strategies (conventional DBS, current steering guided by behavior, and current steering guided by cortical physiology). The extent to which contacts and stimulation parameters are shared among these approaches could be informative and provide a useful internal validation of the current steering approach.

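### The SA2 shared-contact analysis neither defines sharing nor sets a chance reference, so raw sharing between programming strategies cannot be read as internal validation

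*SAP*

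**What the plan says.** At the end of the SA2 text (Sample size for SA2), after the secondary measures, the SAP adds that "we will contrast the probability that active contacts are shared among the programming strategies", namely conventional DBS, steering guided by behaviour and steering guided by cortical physiology. The comment that follows is: "The extent to which contacts and stimulation parameters are shared among these approaches could be informative and provide a useful internal validation". The object of that validation is current steering. The SAP gives no definition of sharing, no agreement statistic, no expected value and no threshold.

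The number of active contacts has to be taken from the protocol:

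- Milestone 2.6 (item 23) ranks the 8 segments and states: "We will simultaneously activate the 3 most highly ranked contact segments for behavioral testing".
- Its rationale fixes the same number for each selection method. The behavioural criteria "will be defined as the 3 lead segments with the lowest floor of the therapeutic window". For physiology: "We will rank and simultaneously activate the 3 most promising lead segments that meet the above criteria based upon P1/N1 peak amplitude".
- Item 16a, on the exploratory crossover arm guided by electrophysiology, leaves the number open: "we will activate a combination of one or more DBS contact segments based purely on electrophysiology from the intraoperative assay". The Crossover Study paragraph of the same item says only that multiple contacts are used.
- No number is fixed for conventional DBS. Items 14 and 19a note that three segments can be activated together as a ring.

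**The concern.** When each of two strategies picks several contacts from a small lead, some overlap is expected even if the two choices have nothing to do with each other. A raw probability of sharing has no meaning until that expectation is known, and the expectation moves with the number of contacts each strategy activates. The planned comparison between pairs of strategies does not supply the missing reference, because the pairs need not have the same contact counts.

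There is a second difficulty. Conventional settings are optimised in the monopolar survey visit, where the therapeutic window of each contact is also measured (protocol item 16a). The behavioural ranking uses those windows (Milestone 2.6), and Table 3 labels both conditions of the two-condition randomised comparison as guided by that survey. Overlap between conventional and behaviour-guided settings is therefore partly dependent by design.

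At stake is the interpretation of a supporting result: a high sharing rate could be reported as reassurance about current steering when it is close to what unrelated choices would give.

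**Working it through.** The documents give no figure for contact sharing, so there is none to reproduce. The check derives the chance reference.

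**Inputs.** 8 segments; 3 active per steering strategy (Milestone 2.6); one or more in the ERP-guided arm (item 16a); 30 participants (SAP, SA2).

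**Formula.** For unrelated sets of n1 and n2 contacts out of 8, the number shared is hypergeometric. Then P(at least one shared) = 1 − C(8−n1, n2)/C(8, n2), and the mean number shared is n1·n2/8.

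**Three versus three.**
- P(at least one) = 1 − C(5,3)/C(8,3) = 1 − 10/56 = 46/56 = 82.1%.
- P(two or more) = (3·5 + 1)/56 = 16/56 = 28.6%.
- P(identical set) = 1/56 = 1.8%.
- Mean number shared = 9/8 = 1.125.

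**In 30 patients.** Expected number sharing at least one = 30 × 46/56 = 24.6, with a central 95% binomial range of 20 to 28. To exceed chance at one-sided 0.05, at least 29 of 30 would have to share a contact: P(29 or more) = 0.021, P(28 or more) = 0.077.

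**Other counts against a three-segment set, at least one shared.**

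| ERP-guided contacts | Calculation | Chance |
|---|---|---|
| 1 | 1 − 35/56 | 37.5% |
| 2 | 1 − 20/56 | 64.3% |
| 3 | 1 − 10/56 | 82.1% |
| 4 | 1 − 4/56 | 92.9% |

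Going from one to three contacts moves the chance value by 82.1 − 37.5 = 44.6 percentage points with no change in agreement.

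**What the number shared offers.** With three versus three, the variance per patient is 3 × (3/8) × (5/8) × (5/7) = 0.502, so the SD is 0.709 and the standard error in 30 patients is 0.709/√30 = 0.129. A mean above 1.125 + 1.96 × 0.129 = 1.38 shared contacts would stand out from chance. This uses more of the data than the yes/no measure, which sits near its ceiling.

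**The case against.** The strongest reply is that this is the last, additional item of SA2, worded cautiously, with no test, threshold, milestone or decision attached. That stands, and it limits the weight of the point. Several stronger readings are tempting and are not supported:

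- *That the SAP would present sharing as validation of the ERP biomarker.* The sentence concerns current steering and says only that sharing could be informative. The biomarker is examined elsewhere, in the SA1.2 regressions and the SA2.3 crossover.
- *That 82% is the chance rate in this trial.* It requires sharing to mean at least one common contact, which the SAP does not say, and three active segments in both sets. The three-segment rule belongs to the Field Shaping Survey. Under other definitions or counts the value is lower or higher, as shown above.
- *That any difference between strategy pairs reflects contact counts.* If both steering sets have three segments, their chance overlap with a given conventional setting is the same, so counts cannot explain a difference between those two pairs. Counts matter only where they differ.
- *That conventional and behaviour-guided settings come from identical readings.* The protocol supports a common visit. Milestone 2.4 compares segments with ring mode and expects differences. The dependence is partial.

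One further objection concerns the remedy. A reference that treats the 8 contacts as interchangeable ignores lead position: both methods may favour the same part of the lead in most patients, and overlap would then exceed n1·n2/8 without any patient-specific agreement. This is right, and the fix needs a second reference for it. The requirement that segments meet the ERP criteria is less of a problem. If the ERP ranking is unrelated to behaviour, filtering leaves the expectation unchanged unless fewer than three segments qualify, and the patient's own count then covers it.

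The SAP sentence also mentions shared stimulation parameters. This calculation does not address them.

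**Conclusion.** The point holds in a limited form. Sharing is undefined and has no chance reference, so the raw probability cannot support a statement about internal validation. Under unrelated choices with three segments each, 82.1% of patients share at least one contact, 28.6% share two or more, and the mean is 1.125. With one or two ERP-guided segments against three, the first figure becomes 37.5% or 64.3%. These values assume that all 8 contacts are equally likely to be chosen; a common preference for certain positions would raise them.

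A reader might infer that the trial's main conclusions are exposed. They are not: the rule of 20 of 30 participants and the sample size do not use this analysis. It is a minor improvement.

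**What to change.** Amend the shared-contact text in the SAP as follows:

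1. Define the measure as the number of active contacts shared per patient for each pair of strategies, and state how a ring is counted in segments.
2. Report observed minus expected, with expected = n1·n2/8 from that patient's own counts, and test the sum over patients against a hypergeometric or within-patient permutation reference.
3. Add a sensitivity reference that pairs each patient's ERP-guided set with other patients' behaviour-guided sets, using the same contact numbering throughout, so that a common preference for certain lead positions is not counted as patient-specific agreement.
4. Base any validation statement on the ERP-versus-behaviour pair. Report pairs that include conventional DBS descriptively, because conventional and behaviour-guided settings both draw on the monopolar survey visit.

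The cost is a few SAP sentences and a short program. It needs no new data, no additional visits, and no change to programming or care.
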